### **2.7.2 Deaths**

Deaths will be described by individual data listings and SAE narratives.

### **2.7.3 Laboratory data**

Blood will be collected throughout the study for standard blood chemistry and hematology tests as well as cardiac enzymes. Urine will be collected throughout the study for standard urinalysis exams.

Hematology variables include: hematocrit, hemoglobin, red blood cell (RBC) count, white blood cell (WBC) count, lymphocytes, neutrophils, lymphocytes, monocytes, eosinophils, basophils, bands, mean corpuscular volume (MCV), mean corpuscular hemoglobin (MCH), mean cell hemoglobin concentration (MCHC), and red cell distribution width (RDW).

Chemistry variables include: albumin, alanine aminotransferase (ALT), alkaline phosphatase, aspartate aminotransferase (AST), blood urea nitrogen (BUN), creatinine, gamma glutamyl

---

transferase (GGT), glucose, serum total bilirubin, direct bilirubin, total creatine kinase (CK), CK-MB, and electrolytes.

Urinalysis variables include: specific gravity, pH, ketones, glucose, protein, blood, leukocyte esterase, nitrites, bilirubin, red blood cell (RBC) count, white blood cell (WBC) count, yeast, squamous epithelial cells, casts, crystals, bacteria.

During the observation period, laboratory data values will be categorized as low, normal, or high based on normal ranges of the laboratory used in this study. A listing will be provided that presents all of the lab values for the patients including meeting PCS criteria during observation Period. PCS criteria are according to the following tables.

**Table 2: Criteria for Potentially Clinically Significant Hematology Values**

Test / Units	Age	Normal Range	Very Low (VL)	Very High (VH)
Hemoglobin (g/dL)	0–3 Days	14.5–22.5 g/dl	<10 g/dl	>24.5
	4–14 Days	12.5–21.5	<10 g/dl	>23.5
	15–59 Days	10–18	<10	>20
	60–89 Days	9–14	<9	>16
	90–179 Days	9.5–13.5	<9.5	>15.5
	180–364 Days	10.5–13.5	<10	>15.5
	1 Year - <2 Years	10.5–13.5	<10	>15.5
	≥2 Years - <6 Years	11.5–13.5	<10	>15.5
	≥6 Years - <12 Years	11.5–15.5	<10	>17.5
	≥12 Years - <18 Years	12–16	<10	>18
Platelets Count (GI/L)	0–6 Days	84–478	<75	
	7–364 Days	130–400	<75	
	≥1 Year	130–400	<75	
White Blood Cell Count (GI/L)	0–3 Days	9.4–34	<3.0	
	4–14 Days	5–21	<3.0	
	15–59 Days	5–19.5	<3.0	
	60–79 Days	5–18	<3.0	
	180–364 Days	5–17	<3.0	
	≥1 Years - <6 Years	5–17	<3.0	
	≥6 Years - ≤12 Years	4.5–13.5	<3.0	

Test / Units	Age	Normal Range	Very Low (VL)	Very High (VH)
Total Neutrophils (absolute, GI/L)	0–3 Days	5–21	<1.5	
	4–14 Days	1.5–0	<1.5	
	15–59 Days	1–9	<1	
	60–89 Days	1–8.8	<1	
	90–179 Days	1–8.5	<1	
	180–364 Days	1.5–8.5	<1.5	
	≥1 Y	1.8–8	<1.5	
Lymphocytes, Absolute (K/µL)	0–3 Days	2–11.5	<0.8	>11.5
	4–14 Days	2–17	<0.8	>17
	15–59 Days	2.5–16.5	<0.8	>16.5
	60–89 Days	3.3–15	<0.8	>15
	90–179 Days	4–13.5	<0.8	>13.5
	180–364 Days	4–10.5	<0.8	>10.5
	≥1 Y	0.85–4.1	<0.8	>4.1
Eosinophils (%)	0–364 Days	0.5–5		>5%
	≥1 Year	0–5		>5%

**Table 3: Criteria for Potentially Clinically Significant Chemistry Values**

Test / Units	Age	Normal Range	Very Low (VL)	Very High (VH)
Alkaline Phosphatase	0–6 Days	40–300		>750
	7–364 Days	50–270		>675
	≥1 - <3 Years	50–270		>675
	≥3 - <13 Years	60–415		1037.5
ALT/SGPT	0–6 Days	0–60		>180
	7–364 Days	0–50		>150
	≤1-<3 Years	0–50		>150
	≥3 Years-<13 Years	0–48		>144
AST/SGOT	0–364 Days	0–60		>180
	≥1 Year - <3 Years	0–60		>180
	≥3 Years - 64 Years	0–42		>126
Total Bilirubin (mg/dL)	0–1 Days	0–6		>9
	2 Days	0–8		>12
	3–5 Days	0–12		>18
	6–90 Days	0–1.3		>1.95
	91–364 Days	0–1.3		>1.95
	≥1 Year	0–1.3		>1.95
Creatinine (mg/dl)	0–2 Days	0.79–1.58		>1.5 X Baseline or >2.37
	3–5 Days	0.46–1.23		>1.5 X Baseline or >1.845
	6–7 Days	0.37–1.05		>1.5 X Baseline or >1.575
	8–30 Days	0.35–0.92		>1.5 X Baseline or >1.38
	31–365 Days	0.27–0.72		>1.5 X Baseline or >1.08
	>1 Year - <4 Years	0.3–0.7		>1.5 X Baseline or >1.05
	≥4 Years - <7 Years	0.29–0.68		>1.5 X Baseline or >1.02
	≥7 Years - <10 Years	0.38–0.73		>1.5 X Baseline or >1.095
BUN (Urea Nitrogen) (mg/dl)	0–6 Days	4–15		>22.5
	7–364 Days	5–18		>27
	≥1 Year - <3 Years	5–18		>27
	≥3 Years - <13 Years	8–21		>31.5
	0–6 Days	30–90	<40	>160

Fasting Glucose (mg/dl)	7–90 Days	60–110	<55	>160
	91–364 Days	60–110	<55	>160
	≥1 Year - <13 Years	60–110	<55	>160
Albumin (G/L)	0–6 Days	20–50	<20	
	7–364 Days	30–50	<30	
	≥1 Year - <3 Years	30–50	<30	
	≥1 - <3 Years	30–50	<30	
	3+ Years	32–50	<30	
GGT	0–6 Days	0–270		>675
	7–364 Days	0–120		>300
	≥1 Year - <3 Years	0–120		>300
	3 Years - 12 Years	0–65		>162.5
Potassium	0–364 Days	3.8–5.5	<3.8	>5.5
	≥1 Year - <3 Years	3.8–5.5	<3.8	>5.5
	≥3 Years - <13 Years	3.5–5.5	<3.5	>5.5
Sodium (mmol/L)	0+ Years	135–146	<135	>155

The Criteria for Potentially Clinically Significant Values will be based upon CTCAE Version 4.03 criteria for Grade 2 or higher adverse event unless otherwise specified.

For hemoglobin and the liver function tests (LFTs) of ALT, AST, alkaline phosphatase, and total bilirubin, patients in each treatment group with a maximum CTCAE Grade of 1, 2, 3, or 4 (see definitions in Table 4) at any post-baseline visit (regardless of the baseline value) through the end of treatment (i.e., Final Treatment Value) will be described. Listings of all ALT, AST, total, indirect and direct bilirubin, and alkaline phosphatase will be created for any patients who had at least a Grade 3 ALT, AST, alkaline phosphatase, or total bilirubin. A listing of hematology results will be provided for patients with hemoglobin abnormalities.

For patients with a Grade 3 or higher total bilirubin elevation, a listing of treatment-emergent adverse events (defined as preferred terms within the "Cholestasis and jaundice of hepatic origin" (broad search) SMQ, excluding preferred terms within the "Investigations" SOC) will be provided.

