2. SYNOPSIS

Name of Sponsor/Company: Novartis Gene Therapies, Inc.	
Name of Investigational Product: AVXS-101	
Name of Active Ingredient: Survival Motor Neuron Gene by Self-Complementary Adeno-Associated Virus Serotype 9 (AAV9)	
Title of Trial: Phase 3, Open-Label, Single-Arm, Single-Dose Gene Replacement Therapy Clinical Trial for Patients with Spinal Muscular Atrophy Type 1 with One or Two SMN2 Copies Delivering AVXS-101 by Intravenous Infusion	
Estimated number of Trial Center(s) and Countries or Regions: Approximately 3 Asian Investigative Sites located in the following countries: Japan, South Korea, Taiwan. Japan is participating in this global study under a Japan-specific version of the AVXS-CL-101-306 protocol.	
Investigators: Multicenter Trial - Investigator Information on File at Novartis Gene Therapies, Inc.	
Studied Period (years): Estimated date first patient enrolled: Q3 2018 Estimated date last patient completed: Q3 2021	Phase of Development: 3
Objectives: Primary 
 Determine efficacy by demonstrating achievement of developmental milestone of sitting without support for at least 10 seconds up to 18 months of age as defined by World Health Organization (WHO) Motor Developmental Milestones. 	
Secondary 
 Determine efficacy based on survival at 14 months of age. Survival is defined by the avoidance of combined endpoint of either (a) death or (b) permanent ventilation which is defined by tracheostomy or by the requirement of \geq 16 hours of respiratory assistance per day (via non-invasive ventilatory support) for \geq 14 consecutive days in the absence of an acute reversible illness, excluding perioperative ventilation. Permanent ventilation, so defined, is considered a surrogate for death. 	
Exploratory 
 [REDACTED] [REDACTED] [REDACTED] [REDACTED] [REDACTED] [REDACTED] [REDACTED] 	

Novartis Gene Therapies, Inc.
Investigational Product: AVXS-101

AVXS-101-CL-306
Protocol Version 6.0/Amendment 5/11 Nov 2020

Safety

- Evaluate the safety of AVXS-101 in patients with SMA Type 1

Methodology:

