7.2. Number of Patients

At least 6 patients was planned to be enrolled as part of the combined analysis with Study AVXS-101-CL-302. At the time of this protocol was amended (Protocol version 6.0 amendment 5 dated 11 Nov 2020), the enrollment was closed with 2 active enrolled patients as the combined analysis is no longer to be performed.

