12. ASSESSMENT OF SAFETY

In the event of unforeseen catastrophe or other, serious situation (such as the COVID-19 pandemic) that occurs during the study, which limits or prevents on-site study visits, regular phone or virtual video calls may occur (as per the Schedule of Assessments) for safety monitoring and discussion of the participant's health status. Visits by site staff/home nursing service to the participant's home, or visits by the participant to a local hospital, laboratory, or imaging center, for performing certain safety assessments, depending on local regulations and capabilities, can replace on-site study visits, if necessary. Analysis of laboratory samples (e.g., chemistry, hematology, urinalysis) may be performed at a local laboratory, if it is not possible to follow the central laboratory process. Other safety assessments that cannot be conducted by telephone (such as vital signs, weight, length, cardiac testing etc.) may similarly be collected by the methods described above.

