12.1.10.2. Blood Chemistry

Samples will be collected and processed by the sites' local laboratories. Blood samples for chemistry analysis will be collected in accord with the SoA ([Appendix 1](#)).

Chemistry analysis will include the following at all trial visits:

- Serum GGT
- AST/ALT
- Serum total bilirubin
- Direct bilirubin
- Albumin
- Glucose
- Creatinine kinase
- Creatinine
- BUN
- Electrolytes (potassium, chloride, CO₂, calcium, inorganic phosphorus, sodium, magnesium)
- Alkaline phosphatase

Patients will have Troponin I collected on the visits specified in the SoA ([Appendix 1](#)).

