## 3 Sample size calculation

The study was originally designed to have sufficient power, when combined with an identically designed study COAV101A12301 (AVXS-101-CL-302), to establish efficacy with regard to the primary and secondary endpoints. Due to the change in data analysis and narrowed scope of COAV101A12304 (OAV101-CL-306), no combined analysis or stand-alone analysis will be conducted.

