### **5.3 Laboratory parameters derivations**

Based on CTCAE grading version 4.0.3, PCS criteria will be derived. Also, Hy's law criteria apply.

[figure not shown]
---

[figure not shown]

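### SAP Table 3 fixes the liver PCS limits to its own printed ULNs although local laboratories run the assays, and the Table 2 white-cell row has no band for 80–179 days

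*SAP*

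**What the plan says.** **Meaning of the flag.** The note under SAP Table 3 reads "The Criteria for Potentially Clinically Significant Values will be based upon CTCAE Version 4.03 criteria for Grade 2 or higher adverse event", and the sentence ends by allowing exceptions where they are specified. SAP 5.3 repeats the rule without that exception: "Based on CTCAE grading version 4.0.3, PCS criteria will be derived". The text of 2.7.3 makes Tables 2 and 3 the operative source of the flag.

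**Grade 2.** SAP Table 4 starts Grade 2 above 3 × ULN for ALT and AST, above 2.5 × ULN for alkaline phosphatase (ALP) and above 1.5 × ULN for total bilirubin. SAP Table 3 gives absolute limits by age, each beside a printed normal range.

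**Who measures.** Protocol 12.1.10.2 says of chemistry: "Samples will be collected and processed by the sites' local laboratories". Section 12.1.10.1 says the same of hematology. The synopsis plans "Approximately 3 Asian Investigative Sites located in the following countries: Japan, South Korea, Taiwan". Protocol section 12, on disruption such as the pandemic, instead says that analysis "may be performed at a local laboratory, if it is not possible to follow the central laboratory process".

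**Which range.** SAP 2.7.3 also says that "laboratory data values will be categorized as low, normal, or high based on normal ranges of the laboratory used in this study". In the readable text it does not say whose ULN Table 4 uses.

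**White cells.** The WBC row of SAP Table 2 goes from 60–79 days straight to 180–364 days.

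**Scale.** Protocol 7.2 records that "the enrollment was closed with 2 active enrolled patients". SAP 2.7.3 lists every laboratory value. It also describes the maximum Table 4 grade for hemoglobin, ALT, AST, ALP and total bilirubin.

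**The concern.** One listing would carry two reference systems. Low, normal and high follow the laboratory's own range, while the PCS flag follows the ranges printed in the SAP. A value could then be Grade 2 on the reporting laboratory's ULN and carry no flag, or be Grade 1 and carry one. The WBC gap is a separate fault in the same set of tables: an age lookup written literally returns no criterion for 80–179 days, and infants in this trial are dosed below 180 days of age.

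Protocol 5.5 names hepatotoxicity as an important identified risk, and the output is patient-level listings and profiles plus three adverse event tables (SAP section 4). A flag said to rest on Grade 2 should therefore track Grade 2. For GGT and WBC there is no Table 4 grade to fall back on. For them the PCS flag is the only severity marker in 2.7.3 beyond low/normal/high.

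**Working it through.** **1. Reproduce the plan's limits.** Limit = Grade 2 multiple (SAP Table 4) × ULN printed in the same row (SAP Table 3).

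- ALT, 3×: 60 → 180; 50 → 150; 50 → 150; 48 → 144.
- AST, 3×: 60 → 180; 60 → 180; 42 → 126.
- ALP, 2.5×: 300 → 750; 270 → 675; 270 → 675; 415 → 1037.5.
- Total bilirubin, 1.5×: 6 → 9; 8 → 12; 12 → 18; then 1.3 → 1.95 in three rows.

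All 4 + 3 + 4 + 6 = 17 limits match exactly. GGT has no Table 4 row, but its four limits are all 2.5 × the printed ULN: 270 → 675; 120 → 300; 120 → 300; 65 → 162.5.

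**2. Let the laboratory's ULN differ.** With multiple m, Grade 2 begins above m × ULN(lab), while the flag begins above m × ULN(printed). If the laboratory's ULN is lower, values between the two bounds are missed. If it is higher, values between them are over-called. If they are equal, there is no error. The documents give no local ULN, so every ULN below other than the printed one is an assumption. The printed limits used are those for 7–364 days (ALT, ALP), 0–364 days (AST) and 91–364 days (bilirubin).

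| Test (fixed flag) | Laboratory ULN | Grade 2 begins above | Result |
|---|---|---|---|
| ALT (>150) | 30 | 3 × 30 = 90 | >90 to 150 missed |
| ALT | 40 | 3 × 40 = 120 | >120 to 150 missed |
| ALT | 50 (printed) | 150 | match |
| ALT | 60 | 3 × 60 = 180 | >150 to 180 over-called |
| AST (>180) | 42 | 3 × 42 = 126 | >126 to 180 missed |
| AST | 72 | 3 × 72 = 216 | >180 to 216 over-called |
| ALP (>675) | 216 | 2.5 × 216 = 540 | >540 to 675 missed |
| ALP | 324 | 2.5 × 324 = 810 | >675 to 810 over-called |
| Bilirubin (>1.95 mg/dL) | 1.04 | 1.5 × 1.04 = 1.56 | >1.56 to 1.95 missed |
| Bilirubin | 1.56 | 1.5 × 1.56 = 2.34 | >1.95 to 2.34 over-called |

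At an assumed ALT ULN of 30, the flag sits at 150/30 = 5 × ULN, which is where Grade 3 begins. The same holds for AST at an assumed ULN of 36 (180/36 = 5).

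**3. The WBC gap.** Days 80 to 179 inclusive: 179 − 80 + 1 = 100 days. For dosing ages tried between 1 and 179 days, 1 to 8 nominal hematology draws (Day -1 onwards) fall inside it. The highest count came from dosing at 90 days of age: the draws at Day -1, 2, 7, 14, 21, 30, 60 and 90 fall at ages 89, 91, 96, 103, 110, 119, 149 and 179 days. All seven printed WBC bands have the same low limit, <3.0, and none has a high limit. Hemoglobin, neutrophils and lymphocytes in the same table all cover 60–179 days.

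**The case against.** The strongest reply is that a fixed table is simply the specified rule. The SAP bases the criteria on Grade 2 and allows exceptions, and it is not pure Grade 2 elsewhere: the low hemoglobin limits are <9 to <10 g/dL at every age, while Table 4 Grade 2 starts at <8.5 g/dL. Fixed limits also treat patients from different laboratories alike. This stands for hemoglobin. It is weaker for the liver tests, where exact agreement in 17 of 17 rows shows that Grade 2 was what the table encoded, and SAP 5.3 states no exception.

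Second, no mismatch is demonstrated. Local ULNs are absent, and the reference-range source under Table 4 is redacted in the public copy, so Tables 3 and 4 may share one set of ranges. Protocol section 12 also treats local testing as a fallback. These points stand as limits on the claim. The specific laboratory sections nevertheless say local, and a central laboratory would raise the same question about whose ULN applies. With 2 patients, at most two of the planned sites contribute.

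Third, other safeguards exist: every value is listed, four liver tests are graded by Table 4, and transaminase elevations are assessed against Hy's Law. This stands, and it keeps the point small. A reader might infer that the flags are the main aid to reading the listings; given these safeguards, the documents do not support that.

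Fourth, the WBC band looks like a misprint with no threshold in doubt. That is fair, but a literal lookup would still return nothing.

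**Conclusion.** The point holds as a minor one. The liver flag equals Grade 2 only where the reporting laboratory's ULN equals the one printed in SAP Table 3. Otherwise it can err in either direction, by an amount that the documents do not let us fix. The WBC row omits 100 days of age and could leave a count below 3.0 unflagged if the table is programmed as printed. The consequence is flag accuracy in listings for 2 patients; no value is lost. If Table 4 is applied with the reporting laboratory's ULN, the grade for ALT, AST, ALP and bilirubin is also intact.

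Two stronger readings should be resisted. A reader might infer that the fixed limits put the flag at odds with the eligibility, prednisolone-taper and Hy's Law thresholds. Eligibility and taper use 2 × ULN, and Hy's Law uses 3 × for transaminases and 2 × for bilirubin. The flag encodes 3 ×, 2.5 × and 1.5 ×, so it would differ from most of these even with local ULNs. It is also a reporting flag and does not feed eligibility or taper. A reader might also infer that the WBC gap can mark values falsely; with no criterion in the gap, it can only miss.

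**What to change.** - In SAP Table 3, replace the absolute limits by the multiples they already encode, applied to the reporting laboratory's age-specific ULN: ALT >3 ×, AST >3 ×, ALP >2.5 ×, GGT >2.5 ×, total bilirubin >1.5 ×.
- State in SAP 2.7.3 that the same ULN source is used for Table 4 grades and the Hy's Law assessment.
- In SAP Table 2, change the WBC row 60–79 days to 60–179 days and leave <3.0 as it is.
- Reconcile Protocol section 12 with 12.1.10.1 and 12.1.10.2 on whether chemistry and hematology are run locally or centrally.

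The cost is table wording and a small programming change. The laboratory ranges needed are those that the low/normal/high classification already requires. No new data are collected and no WBC threshold moves.

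### SAP Table 2 flags hemoglobin 0.5 to 1.5 g/dL above where SAP Table 4 starts Grade 2, with no exception marked; separately, the newborn glucose limit in Table 3 overlaps its printed normal range

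*SAP*

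**What the plan says.** SAP Section 2.7.3 plans a listing of all laboratory values that shows which meet PCS criteria, and takes those criteria from Tables 2 and 3. The note under Table 3 gives their basis: they "will be based upon CTCAE Version 4.03 criteria for Grade 2 or higher adverse event unless otherwise specified". SAP Section 5.3 repeats the link to CTCAE, without naming a grade and without the exception clause: "Based on CTCAE grading version 4.0.3, PCS criteria will be derived".

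Table 2, "Criteria for Potentially Clinically Significant Hematology Values", prints for each hemoglobin age band a normal range and a very low limit. Four of the ten rows read, in order of age, normal range and limit: "15–59 Days 10–18 <10", "60–89 Days 9–14 <9", "90–179 Days 9.5–13.5 <9.5" and "180–364 Days 10.5–13.5 <10". The other six bands also use a limit of 10 g/dL.

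Table 4 defines CTCAE Grades 1 to 4 for five tests: ALT, AST, alkaline phosphatase, total bilirubin and hemoglobin. For hemoglobin, Grade 1 runs from the lower limit of normal (LLN) down to 8.5 g/dL, Grade 2 from below 8.5 to 7.5, Grade 3 from below 7.5 to 5, and Grade 4 is below 6.5. Section 2.7.3 also plans to describe patients by their maximum grade on these tests.

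For glucose at 0–6 days, Table 3 prints a normal range of 30–90 mg/dL and a very low limit of below 40.

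**The concern.** A limit said to rest on Grade 2 should sit where the same SAP starts Grade 2. For hemoglobin it sits higher at every age. The PCS listing and the graded description would then give different accounts of the same blood result, and a reader of the report could not tell whether a flagged hemoglobin had reached Grade 2. The glucose row raises a separate question: a limit for very low should not lie inside the range printed as normal on the same line.

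**Working it through.** **Inputs.** Normal ranges and PCS limits come from SAP Tables 2 and 3, and grade boundaries from SAP Table 4.

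**Step 1: does the Grade 2 rule reproduce where it can be tested?** For the liver tests, expected limit = printed upper limit of normal (ULN) × the multiple at which Table 4 starts Grade 2.

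| Test | Multiple | Printed ULN → expected limit | Printed limit |
|---|---|---|---|
| Alkaline phosphatase | 2.5 | 300 → 750; 270 → 675; 415 → 1037.5 | 750; 675; 1037.5 |
| ALT | 3 | 60 → 180; 50 → 150; 48 → 144 | 180; 150; 144 |
| AST | 3 | 60 → 180; 42 → 126 | 180; 126 |
| Total bilirubin | 1.5 | 6 → 9; 8 → 12; 12 → 18; 1.3 → 1.95 | 9; 12; 18; 1.95 |

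All 12 distinct limits agree, so the stated rule was applied to these four tests.

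**Step 2: the fifth test in Table 4.** Gap = Table 2 limit − 8.5 g/dL.

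| Age band | Printed LLN | Table 2 limit | Gap over 8.5 |
|---|---|---|---|
| 0–3 days | 14.5 | <10 | 1.5 |
| 4–14 days | 12.5 | <10 | 1.5 |
| 15–59 days | 10 | <10 | 1.5 |
| 60–89 days | 9 | <9 | 0.5 |
| 90–179 days | 9.5 | <9.5 | 1.0 |
| 180–364 days | 10.5 | <10 | 1.5 |
| 1 to <2 years | 10.5 | <10 | 1.5 |
| 2 to <6 years | 11.5 | <10 | 1.5 |
| 6 to <12 years | 11.5 | <10 | 1.5 |
| 12 to <18 years | 12 | <10 | 1.5 |

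No band matches. At 15–59, 60–89 and 90–179 days the limit equals the printed LLN, which is where Table 4 starts Grade 1.

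As an illustration, take 9.2 g/dL at 200 days of age. It is below 10, so it is PCS. It is below the printed LLN of 10.5 and not below 8.5, so it is Grade 1.

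**Step 3: is Table 4 a sound yardstick?** Its Grade 3 covers below 7.5 down to 5, and its Grade 4 covers everything below 6.5. Values from 5 to below 6.5 g/dL fall in both grades; 6.0 is an example. At least one cell in that row is wrong.

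**Step 4: glucose.** Overlap = very low limit − lower normal limit, where positive.

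- 0–6 days: 40 − 30 = 10 mg/dL, out of a normal range 90 − 30 = 60 mg/dL wide (16.7%).
- 7–90 days, 91–364 days and from 1 year: 55 is below 60, so there is no overlap.

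Only the newborn row conflicts with itself.

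**The case against.** The strongest defence is the clause that lets the tables specify otherwise. Section 2.7.3 says the criteria are those in the tables, so an explicit age-specific limit might itself count as the exception, and Table 2 never calls its limits grade boundaries. Other rows point the same way. The limits for low sodium, for low and high potassium, for high lymphocytes and for high eosinophils all sit at the printed normal limit, which is where Table 4 starts Grade 1 for its own tests. The tables may have been built on a mixed basis.

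That possibility stands, and the fix allows for it. It does not remove the conflict. No hemoglobin row or footnote states another basis, and Section 5.3 ties the criteria to CTCAE with no exception. The note is printed under the chemistry table, but its wording covers PCS values generally.

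It also stands that the listing shows every laboratory value, so nothing is hidden. Section 2.7.3 classes values as low, normal or high by the laboratory's own ranges, which are not in the documents. How the glucose overlap would look on a listing therefore depends on those ranges. Likewise, if grading used a laboratory LLN lower than the printed one, a flagged hemoglobin of 8.5 g/dL or more could be ungraded instead of Grade 1. It would still not be Grade 2.

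A reader might infer three stronger points that the documents do not support:

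- **That 8.5 g/dL is right and Table 2 wrong.** Table 4's hemoglobin row is visibly faulty, so it may be the one in error.
- **That the glucose limit also breaches Grade 2.** The SAP gives no CTCAE grade for glucose. The conflict is only with the printed normal range, and either cell could be wrong.
- **That the fasting label is wrong because samples are taken non-fasting.** Protocol Section 12.1.10.2 lists glucose without saying either way, and Section 12.1.10 leaves collection to laboratory manuals. There is no basis for asking for new non-fasting limits.

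**Conclusion.** The hemoglobin point holds. Under the stated rule, and with no exception marked, Tables 2 and 4 disagree in all ten age bands. Values in conflict run from 8.5 g/dL up to 10 at 0–59 days and from 180 days, up to 9 at 60–89 days, and up to 9.5 at 90–179 days. The bands from 180 days matter most in practice, because every infant followed to the 18-month visit (540 days) passes through them. The break is not general: the four liver tests conform.

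The newborn glucose row is a separate and smaller inconsistency. In the available text that row is printed just before the fasting glucose label. Assigning it to glucose is an inference, but a safe one: urea nitrogen already has its own 0–6-day row, and the upper limit of 160 matches the other glucose rows.

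The consequence is minor. Enrollment closed with two patients (Protocol Section 7.2), the laboratory output is mainly listings, and no efficacy endpoint depends on these flags. The glucose row matters only if a sample was taken in the first week of life. This is a correction worth making, not a threat to the trial's conclusions.

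**What to change.** 1. Check all four hemoglobin grade boundaries against CTCAE 4.03 and correct the Table 4 row, including the overlap of Grades 3 and 4.
2. Reconcile the Table 2 hemoglobin limits with the corrected row. If another basis was intended, mark in Table 2 each row that deliberately departs from Grade 2 and say what it rests on. The same marking would serve the rows in Tables 2 and 3 that sit at the normal limit.
3. Reconcile the lower normal limit and the very low limit in the 0–6-day glucose row against the source of the ranges, without presuming which cell is wrong.

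The cost is a few SAP table cells or a footnote, and a matching edit to the program that sets the flags. No data collection changes.

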11. Anti-AAV9 antibody titer > 1:50 as determined by Enzyme-linked Immunosorbent Assay (ELISA) binding immunoassay. Should a potential patient demonstrate Anti-AAV9 antibody titer > 1:50, he or she may receive retesting within 30 days of the screening period and will be eligible to participate if the Anti-AAV9 antibody titer upon retesting is ≤ 1:50
12. Clinically significant abnormal laboratory values GGT, ALT, AST, total bilirubin >2x the ULN, creatinine ≥ 1.0 mg/dL, hemoglobin [Hgb] < 8 or > 18 g/dL; white blood cell [WBC] > 20,000 per cmm) prior to gene replacement therapy. Patients with an elevated bilirubin level that is unequivocally the result of neonatal jaundice shall not be excluded.
13. Participation in recent SMA treatment clinical trial (with the exception of observational cohort studies or non-interventional studies) or receipt of an investigational or commercial compound, product or therapy administered with the intent to treat SMA (e.g., nusinersen, valproic acid) at any time prior to screening for this trial. Oral beta-agonists must be discontinued at least 30 days prior to dosing. Inhaled albuterol specifically prescribed for the purposes of respiratory (bronchodilator) management is acceptable and not a contraindication at any time prior to screening for this trial
14. Expectation of major surgical procedures during the trial assessment period (e.g., spinal surgery or tracheostomy)
15. Parent(s)/legal guardian(s) unable or unwilling to comply with trial procedures or inability to travel for repeat visits
16. Parent(s)/legal guardian(s) unwilling to keep trial results/observations confidential or to refrain from posting confidential trial results/observations on social media sites
17. Parent(s)/legal guardian(s) refuses to sign consent form
18. Patients < 35 weeks gestational age at time of birth

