**Table 4: Definitions of CTCAE Grades 1, 2, 3, and 4**

Test	Grade 1	Grade 2	Grade 3	Grade 4
ALT/SGPT	>ULN – 3 × ULN	>3–5 × ULN	>5–20 × ULN	>20 × ULN
AST/SGOT	>ULN – 3 × ULN	>3–5 × ULN	>5–20 × ULN	>20 × ULN
Alkaline phosphatase	>ULN – 2.5 × ULN	>2.5–5 × ULN	>5–20 × ULN	>20 × ULN
Total bilirubin	>ULN – 1.5 × ULN	>1.5–3 × ULN	>3–10 × ULN	>10 × ULN
Hemoglobin decreased	<LLN – 8.5 g/dL	<8.5–7.5 g/dL	<7.5–5 g/dL	<6.5 g/dL

Reference Ranges, [REDACTED]

In order to assess hepatotoxicity, all elevations in liver transaminases are evaluated using Hy's Law criteria as these help to determine the risk of drug-induced liver injury. All elevations in liver transaminases will be assessed against these criteria. Hy's Law cases have the following three components:

1. The drug causes hepatocellular injury, generally shown by a higher incidence of 3-fold or greater elevations above the ULN of ALT or AST than the (non-hepatotoxic) control drug or placebo;
2. Among trial patients showing such aminotransferase (AT) elevations, often with ATs much greater than 3×ULN, one or more patients also shows elevation of serum total bilirubin (TBL) to  $\geq 2 \times$ ULN, without initial findings of cholestasis (elevated serum ALP);
3. No other reason can be found to explain the combination of increased AT and TBL, such as viral hepatitis A, B, or C, pre-existing or acute liver disease, or another drug capable of causing the observed injury [FDA (2009)].

For patients enrolled in this study these criteria are assessed in order to determine both general liver function enzyme changes (LFEs) according to change from baseline and over course of study. In addition, the assessment of changes in ALT or AST relative to TBL allowed assessment if a signal related to DILI occurred in any individual or group of patients.

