## 4 Change to protocol specified analyses

Due to the narrowed scope of COAV101A12304 (AVXS 101 CL 306) and limited subjects enrolled, only individual data listings and patient profiles will be generated, with the exception of three AE summary tables. There are no changes to analyses planned in protocol version 6.0.

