### **5.2 AEs coding/grading**

AEs are encoded according to the latest version of MedDRA available at the start of the study. CTCAE grading version 4.0.3 applies.

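### SAP Table 4 prints overlapping hemoglobin limits for Grades 3 and 4, so a value from 5 to <6.5 g/dL meets both and the grading rule does not separate them

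*SAP*

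**What the plan says.** The paragraph after Table 3 in SAP section 2.7.3 sets the rule. It opens "For hemoglobin and the liver function tests (LFTs) of ALT, AST, alkaline phosphatase, and total bilirubin" and describes patients "with a maximum CTCAE Grade of 1, 2, 3, or 4 (see definitions in Table 4) at any post-baseline visit". Table 4 is therefore the working definition of the hemoglobin grades, not background.

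The hemoglobin row of Table 4 gives Grade 1 as below the lower limit of normal down to 8.5 g/dL and Grade 2 as below 8.5 down to 7.5. The Grade 3 and Grade 4 cells, side by side, read "<7.5–5 g/dL <6.5 g/dL".

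No other part of either document gives hemoglobin limits by grade. SAP section 5.2 says "CTCAE grading version 4.0.3 applies" but does not reproduce that version's limits. Protocol section 13.1.1 gives only the general CTCAE severity descriptions. Neither document says which source prevails if Table 4 and CTCAE differ.

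**The concern.** A grading table should assign each abnormal value to one grade. Here a hemoglobin of 6.0 g/dL satisfies the printed definitions of both Grade 3 and Grade 4. A program that tests Grade 3 first returns Grade 3, and one that tests Grade 4 first returns Grade 4. Both follow the table.

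At stake is whether a prespecified safety grade can be reproduced. With two patients, each grade is reported individually, so no aggregate would dilute a wrong label.

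**Working it through.** **1. Inputs.** The Table 4 limits are taken as printed. Lower limits are read as inclusive, because Grade 2 stops at 7.5 and Grade 3 starts below 7.5.

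**2. Do the grades meet?** For each test, compare the end of one grade with the start of the next.

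| Test | Grade 1/2 | Grade 2/3 | Grade 3/4 |
|---|---|---|---|
| ALT (× ULN) | 3 | 5 | 20 |
| AST (× ULN) | 3 | 5 | 20 |
| Alkaline phosphatase (× ULN) | 2.5 | 5 | 20 |
| Total bilirubin (× ULN) | 1.5 | 3 | 10 |
| Hemoglobin (g/dL) | 8.5 | 7.5 | Grade 3 ends at 5, Grade 4 starts below 6.5 |

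There are 5 × 3 = 15 boundaries. Fourteen meet at a single number and one does not.

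**3. Size of the overlap.** 6.5 − 5 = 1.5 g/dL. The printed Grade 3 range is 7.5 − 5 = 2.5 g/dL, so the overlap is 1.5 / 2.5 = 60% of it.

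**4. Value by value.** Hemoglobin from 3.0 to 10.9 g/dL was graded in steps of 0.1, with a lower limit of normal of 10.5 (SAP Table 2, 180–364 days). Every value from 5.0 to 6.4 meets Grades 3 and 4. No other value meets two grades, and no value below 10.5 is ungraded.

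**5. What a correction would do.** Two single edits each remove the overlap and leave no gap:

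| Edit | 4.9 | 5.0 to 6.4 | 6.5 |
|---|---|---|---|
| Grade 4 starts below 5 | Grade 4 | Grade 3 | Grade 3 |
| Grade 3 ends at 6.5 | Grade 4 | Grade 4 | Grade 3 |

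They give opposite grades for the whole disputed band, so the choice cannot be left to the programmer.

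**6. What else depends on the split?**

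- *Hemoglobin listing.* "A listing of hematology results will be provided for patients with hemoglobin abnormalities", with no grade threshold.
- *Grade 3 listing trigger.* The listing in section 2.7.3 that requires Grade 3 or higher covers liver tests only.
- *Potentially clinically significant (PCS) flag.* Section 2.7.3 says "PCS criteria are according to the following tables". The very-low hemoglobin limits in Table 2 are 9, 9.5 or 10 g/dL depending on age, so every value in the band is flagged under either grade.
- *Adverse event overview.* SAP section 2.7.1 pools Grades 3 and 4.
- *Laboratory output.* Section 2.7.3 lists all laboratory values, so the measured hemoglobin is visible whatever its grade.

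**7. Can the band be reached?** Exclusion criterion 12 in Protocol section 8.2 bars "hemoglobin [Hgb] < 8 or > 18 g/dL" before gene therapy. From the lowest eligible level, a value in the band needs a fall of more than 8 − 6.5 = 1.5 g/dL. Nothing in the documents shows that this happened.

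**The case against.** **The word *maximum* settles it.** If a value meets Grades 3 and 4, the higher grade is Grade 4. This is a natural reading, but the rule ties the maximum to post-baseline visits and does not mention a single value with two grades. If it is applied within a value, everything below 6.5 becomes Grade 4 and the printed Grade 3 limit of 5 never operates. The table would still need correction.

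**It may be a PDF-reading error.** This stands as a possibility. Table 2 has other doubtful entries, such as a neutrophil range of 1.5–0 and a white-cell age band of 60–79 days followed directly by 180–364 days. Against this, both hemoglobin cells are complete, with sign, number and unit. Table 3 has slips that character loss does not readily explain, such as an albumin age row that appears twice. Neither origin is proved.

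**It changes nothing that matters.** Largely accepted. SAP section 4 says "only individual data listings and patient profiles will be generated, with the exception of three AE summary tables", enrollment closed at two patients, and step 6 of the working found no other output that moves. This limits the weight of the point but does not make the definition usable.

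**A tempting stronger reading is that the 5 must be the misprint.** A Grade 3 range ending at 6.5 would be 7.5 − 6.5 = 1.0 g/dL wide, the same as Grade 2 (8.5 − 7.5 = 1.0). But equal widths are not this table's pattern: for ALT, Grade 2 spans 5 − 3 = 2 × ULN and Grade 3 spans 20 − 5 = 15 × ULN. The source line under Table 4 is partly redacted and the CTCAE limits are not reproduced, so the documents do not identify the faulty limit. Nor do they show that only one is faulty.

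**Conclusion.** The point holds as an internal contradiction in an operative definition. As printed, hemoglobin from 5 to <6.5 g/dL is both Grade 3 and Grade 4, no rule separates them, and at least one limit is wrong.

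The consequence is minor. Only the Grade 3 versus Grade 4 hemoglobin label could differ, for at most two patients and only if a value fell in the band. A reader might infer that safety results are misreported or that a signal could be hidden. The documents do not support that: every value in the band is Grade 3 or higher either way, is flagged as PCS either way, and is listed with its measured value.

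The conclusion assumes that the table was read correctly from the PDF, which only the original can confirm. It uses no CTCAE limit from outside the documents.

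**What to change.** Check the hemoglobin row of Table 4 against the original SAP file and against CTCAE 4.03, the version the SAP cites. If the overlap is in the original, reconcile the row so that Grade 3 ends where Grade 4 begins. Do this before hemoglobin grades are derived. If they already exist, rerun that derivation for the two patients.

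No new data are needed, and no analysis outside the hemoglobin grade derivation is touched. How many cells change depends on what the check finds.
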